4.11.3 Deaths, Serious Adverse Events, and Other Significant Adverse Events

SAE

An SAE is defined as one of the following:

- Is fatal
- Is life-threatening
- Results inpatient hospitalization or prolongation of existing hospitalization
- Results in a persistent or significant disability/incapacity
- Constitutes a congenital anomaly/birth defect
- Is medically significant, i.e., defined as an event that jeopardizes the patient or may require medical or surgical intervention to prevent one of the outcomes listed above
- Note that hospitalizations for the following reasons should not be reported as SAEs:
 - Routine treatment or monitoring of the studied indication, not associated with any deterioration in condition.
 - Elective or pre-planned treatment for a pre-existing condition that is unrelated to the indication under study and has not worsened since signing the informed consent.

- Social reasons and respite care in the absence of any deterioration in the patient's general condition.
- Note that treatment on an emergency outpatient basis that does not result in hospital admission and involves an event not fulfilling any of the definitions of a SAE given above is not an SAE.

AE Summaries by System Organ Class and Preferred Term

The incidence for the following will be summarized by SOC and PT, unless otherwise specify:

- SAEs
- SAEs Related to Study Drug
- SAEs with Outcome Fatal
- TEAEs Leading to Study Drug Discontinuation

Separate tables for on-treatment period and safety follow up period will be provided, and below by-subject listings will be provided:

- All SAEs
- All Fatal SAEs
- All AEs leading to Study Drug Discontinuation

Adverse Events of Special Interest (AESI)

Adverse events of special interest to be monitored include gastrointestinal, cardiovascular, hepatic, and neurological adverse events (dizziness, headache), hematological (anemia, leukopenia, neutropenia) and elevated creatinine kinase. (Appendix 6.5)

TEAEs of special interest will be summarized by SOC and PT.

Time to TEAEs of Special Interest

Time to TEAEs of special interest (in days) is defined as:

First date when TEAEs of special interest onset - first dosing date + 1.

If a patient has not experienced TEAEs of special interest by completion or early discontinuation of study/study treatment, the patient will be censored at the date of their last visit.

Time to TEAEs of special interest will be summarized for Safety set using the Kaplan-Meier (KM) method. Log-rank test will be used. P-values and hazard ratios with 95% confidence intervals based on Cox proportional hazard model stratified by duration since symptom onset to randomization category (≤ 3 days; > 3 days) will be present.

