### **GT0918-CN-1003**

The GT0918-CN-1003 was an open-label, randomized, Phase 2, multicenter study to evaluate the safety and efficacy in subjects with mCRPC. Total of 108 subjects were enrolled in the study and randomized in 1:1:1 ratio in to 100 mg, 200 mg and 300 mg cohorts: 100 mg (n=37), 200 mg (n=35) and 300 mg (n=36). Eighty-one subjects (75.0%) experienced  $\geq$  grade 1 drug-related AEs. Fourteen subjects (13.0%) experienced  $\geq$  Grade 3 AEs based on CTCAE v4.03. Most common drug-related AEs experienced  $\geq$  10% of subjects included aspartate aminotransferase increased (AST) (14.8%), alanine aminotransferase increased (ALT) (13.0%), white blood cell count decreased (12.0%), appetite decreased (13.0%), asthenia (17.6%), anemia (14.8%) and proteinuria (12.0%). Grade 3 asthenia, Grade 2 vomiting, Grade 2 hypokalemia, Grade 2 lung infection, Grade 3 anemia were the reported SAEs among all subjects. There were about 41.9% subjects who experienced Prostate-Specific Antigen (PSA) 50 reduction. Based on Response Evaluation Criteria in Solid Tumors (RECIST) 1.1 evaluation, the Overall Response Rate (ORR) was 15.8% and Disease Control Rate (DCR) was 78.9%.

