## **8.2 Adverse Events of Special Interest (AESI)**

The Adverse events of special interest (AESI) search table will be used to map reported AEs to the notable AE groupings. AESI could be updated during the course of study based on accumulating safety data. Therefore the clinical study report includes the AE groupings (such as gastrointestinal disorders, cardiovascular disorders, increased liver transaminase, and neurological disorders, peripheral blood cytopenia and renal disorders). used and provide a listing of the corresponding AESI search table. AESI will be summarized regardless of study drug relationship, by grouping, PT and treatment arm.

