6.3 Clinical Laboratory Parameters**Table 5 Clinical Laboratory Parameters**

Test category	Local/Central	Test Name
Hematology	Local	Hemoglobin Hematocrit Erythrocyte count (RBCs - Red Blood Cells) Leukocytes (WBCs - White Blood Cells) Differential Neutrophils, segmented Lymphocytes Monocytes Eosinophils Basophils Platelets
Clinical Chemistry	Local	Sodium Potassium Chloride Bicarbonate Total bilirubin Direct bilirubin Alkaline phosphatase (ALP) Alanine aminotransferase (ALT) Aspartate aminotransferase (AST) Gamma-glutamyl transferase (GGT) Blood urea nitrogen (BUN) Creatinine Creatine kinase (CK) Uric acid Total protein Albumin Calcium Phosphorus Glucose Amylase Lipase Lactate dehydrogenase (LDH)
Coagulation	Local	International normalized ratio (INR), partial thromboplastin time: non-activated (PTT) or activated (aPTT)
Additional tests	Local/Central*	C-reactive protein (CRP); high-sensitivity Ferritin D-dimer Procalcitonin Troponin (preferably Troponin I)

Parexel International

Suzhou Kintor Pharmaceuticals, Inc.
GT0918-US-3001

Statistical Analysis Plan

Test category	Local/Central	Test Name
Virology	Central	SARS-CoV-2 viral infection determination at screening - local SARS-CoV-2 viral load test (quantitative ddPCR) - central
Pharmacokinetic Analyses	Central	Analyzed using validated LC-MS/MS methods with a LLOQ of approximately 5.00 ng/mL for GT0918
Hormones (Male &Female)	Central	Testosterone
Hormones (Female)	Local	Serum Pregnancy Urine Pregnancy

* Central laboratories will be used when it can't be tested on local laboratory.

6.4 Subject Questionnaire1. What was the severity of your stuffy or runny nose at its worst over the last 24 hours?

None =0	Mild =1	Moderate =2	Severe =3
------------	------------	----------------	--------------

2. What was the severity of your sore throat at its worst over the last 24 hours?

None =0	Mild =1	Moderate =2	Severe =3
------------	------------	----------------	--------------

3. What was the severity of your shortness of breath (difficulty breathing) at its worst over the last 24 hours?

None =0	Mild =1	Moderate =2	Severe =3
------------	------------	----------------	--------------

4. What was the severity of your cough at its worst over the last 24 hours?

None =0	Mild =1	Moderate =2	Severe =3
------------	------------	----------------	--------------

5. What was the severity of your Low energy or tiredness at its worst over the last 24 hours?

None =0	Mild =1	Moderate =2	Severe =3

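### SAP 4.11.3 drops the renal grouping that Protocol 8.2 gives for adverse events of special interest, records no reason, and omits the by-grouping summary

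*SAP*

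**What the plan says.** Protocol 8.2 describes the AESI groupings for the clinical study report by example: "such as gastrointestinal disorders, cardiovascular disorders, increased liver transaminase, and neurological disorders, peripheral blood cytopenia and renal disorders". It specifies the output, "AESI will be summarized regardless of study drug relationship, by grouping, PT and treatment arm", and leaves room for revision: "AESI could be updated during the course of study based on accumulating safety data".

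SAP 4.11.3 states the AESI to be monitored as "gastrointestinal, cardiovascular, hepatic, and neurological adverse events (dizziness, headache), hematological (anemia, leukopenia, neutropenia) and elevated creatinine kinase" and refers to Appendix 6.5 for the search terms. On layout it says "TEAEs of special interest will be summarized by SOC and PT". The same section defines time to AESI as days from first dose to first AESI onset and censors subjects without one at their last visit. It then applies Kaplan-Meier, log-rank and Cox methods on the Safety set. SAP 4.11.2 also puts a line for treatment-emergent AESI in the adverse event overview table.

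Protocol 10.1 says that the SAP prevails where the two documents differ.

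**The concern.** The narrower list governs the report, because the SAP takes precedence. Membership of that list decides three things: who is counted in the AESI overview line, who is counted in the AESI table, and who has an event in the time-to-AESI comparison. That comparison is the only between-arm time-to-event test the SAP plans for safety. Leaving out a grouping that the protocol names changes what all three outputs measure.

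The change is also undocumented. The SAP revision history goes down to p-value decimals and the toxicity grade for aPTT but has no AESI entry. Where the SAP knowingly departs from the protocol on missing primary data, it gives a dedicated justification (4.10.1.1.3). Nothing comparable exists here, so a reader of the study report could not tell a considered update from an oversight.

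**Working it through.** The plan gives no figure on this point, so the check is a comparison of text.

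**Step 1. Match the groupings.**

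| Protocol 8.2 | SAP 4.11.3 |
|---|---|
| Gastrointestinal | Present |
| Cardiovascular | Present |
| Liver transaminase | Present (as hepatic) |
| Neurological | Present |
| Blood cytopenia | Present (as hematological) |
| Renal | **Absent** |
| Not named | CK added |

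Five of the six protocol examples carry over, one does not, and one category is new.

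**Step 2. Is the added item a renal one under another name?** SAP 4.11.3 spells it as creatinine kinase. SAP Table 5 lists "Creatine kinase (CK") as its own chemistry test, separate from creatinine. The item is the muscle enzyme, not a kidney measure.

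**Step 3. Look for renal terms in the search list.** Appendix 6.5, as available to us, covers liver; red cell, white cell, platelet and multi-lineage cytopenias; agranulocytosis; gastrointestinal inflammation and dysfunction; arrhythmia; and torsade/QT. It has no renal group and no renal preferred term. The two urine bilirubin terms belong to the liver group.

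**Step 4. Follow a subject whose only candidate event is renal.**
- Overview line (4.11.2): not counted.
- AESI table (4.11.3): not counted.
- Time to AESI (4.11.3): censored at the last visit, so treated as event-free in the log-rank test and the Cox model.
- A subject with an early renal event and a later AESI of another kind is dated from the later one.

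**Step 5. Check where the event still appears.**
- Treatment-emergent event tables by class and term, including those for related events, Grade 3 or higher, and maximum grade (4.11.2).
- Serious event and discontinuation tables, where applicable (4.11.3).
- Creatinine and blood urea nitrogen are scheduled chemistry tests (Table 5) and fall under the Grade 3 or 4 frequency tables and the baseline-to-worst shift tables (4.11.4.1).

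**Step 6. Compare the layouts.** Protocol 8.2 asks for grouping, preferred term and arm. SAP 4.11.3 gives class and preferred term. A class-by-term layout does not give the number of subjects with at least one event in a grouping unless the grouping happens to coincide with a class. Adding renal terms alone would therefore not supply the renal-group count that the protocol describes.

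**The case against.** The strongest reply is that the protocol sets no fixed list. Its groupings are introduced as examples, it allows updates, and the SAP overrides it. With CK added, the SAP list looks like a revision, and its own verb, include, is not strictly exhaustive. All of this stands as a matter of permission, and a reader should not infer that a binding list of six was breached. It does not explain why one named grouping left while the other five stayed. The protocol ties updates to accumulating safety data, and neither document reports such data on renal events or records an update.

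Second, the check of Appendix 6.5 is limited. Text following the supplied table was not available to us. The supplied table also has no term for CK, dizziness or headache, although 4.11.3 names all three. Either the list continues in text we have not seen, or the appendix has wider gaps. The sentence in 4.11.3 is complete, however, and omits renal either way.

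Third, the evidence for a renal signal is modest. Protocol 1.3.3 names renal function among the assessments used to monitor key toxicities, not as a toxicity itself; coagulation is named there too and is an AESI grouping in neither document. The earlier COVID-19 outpatient study (1.2.3.2) describes no renal event among its frequent or drug-related events. The Phase 2 prostate cancer study does list "anemia (14.8%) and proteinuria (12.0"%) among common drug-related events.

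A reader might apply that proteinuria rate to an arm of 334 and infer about 40 affected subjects (0.12 x 334 = 40). The documents do not support this. The rate comes from an open-label oncology study pooling 100, 200 and 300 mg, with treatment and population unlike this trial's. The laboratory plan here schedules no urinalysis, so proteinuria would surface only through unscheduled testing.

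**Conclusion.** The point holds as a minor safety-reporting correction. SAP 4.11.3 omits the renal grouping without a recorded update or reason and reports AESI in a different layout from the one Protocol 8.2 requires. Renal-only events are excluded from the AESI overview line and table and count as no event in the time-to-AESI analyses.

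The size is one of six example groupings plus the missing by-grouping summary. No number of subjects is claimed, because the documents give no usable renal event rate for this setting.

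A reader might go further and conclude that renal events vanish from the safety report. They do not: the general event tables and the creatinine and urea nitrogen tables keep them. No efficacy or stopping rule described in the two documents uses the AESI results, and the primary analysis is unaffected.

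The conclusion assumes that the list in 4.11.3, with Appendix 6.5, is what will be programmed, and that any unseen remainder of the appendix contains no renal terms. If it does contain them, the gap narrows to the wording of 4.11.3 and the layout.

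**What to change.** 1. Add a renal group to the AESI list in SAP 4.11.3 and a matching renal term list to Appendix 6.5, after checking any part of the appendix not seen here.
2. Summarise AESI by grouping as well as by preferred term and arm, as Protocol 8.2 requires. Appendix 6.5 already assigns each term to a named group, so the structure exists.
3. If renal was removed on accumulating safety data, state that reason in the SAP instead of making change 1. Change 2 is needed in either case.
4. While the appendix is open, confirm that it contains terms for CK, dizziness and headache, which 4.11.3 names.

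The cost is an SAP amendment, a search-list entry and some reprogramming of the AESI outputs. No new data and no protocol change are needed. The AESI total may rise, and the time-to-AESI results may move accordingly. The amendment should precede unblinding; if that is no longer possible, the added renal outputs should be labelled as specified afterwards.

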4.11.4 Clinical Laboratory Evaluation

Local clinical laboratory parameters will be used for the analysis of scheduled hematology, chemistry and other blood specimens collected as part of safety monitoring (as detailed in SoA), except for specific parameters which will be performed centrally. For a list of the parameters to be evaluated, see Table Clinical Laboratory Parameters in appendices.

For parameters where a DAIDS Version 2.1 scale exists, laboratory results will be graded according to DAIDS Version 2.1 toxicity grade. A Grade 0 will be assigned for all non-missing values not

graded as 1 or higher. For laboratory tests where grades are not defined by DAIDS, results will be graded by the low/normal/high classifications based on laboratory normal ranges.

A single measure for partial thromboplastin time (PTT) will be collected and both non-activated and activated PTT (aPTT) can be captured in the measure. DAIDS toxicity grading scale for partial thromboplastin time (PTT) will be used for the PTT/aPTT measure.

Laboratory values obtained during the screening phase will be used to assess subject's eligibility, and therefore it will be listed only, but not summarized in tables.

Laboratory values reported as a character value, such as <40, will be transformed into numerical values for summary reasons.

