### **7.2.2 Safety and Tolerability Assessments**

Safety assessments are specified below with the assessment schedule detailing when each assessment is to be performed.

For safety evaluations, baseline is defined as assessments done on Day 1 prior to the first dose of study treatment.

The investigator will report any vital signs considered clinically significant in the eCRF. For details on AE collection and reporting refer to AE [Section 8.1](#).

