4.2 General Presentation Considerations

Baseline: the last available pre-treatment assessment, unless otherwise specified.

For subjects who are screened, randomized, and undertake the first treatment on the same date, the self-reported symptom questionnaire and ordinal scale at Day 1 visit will be flagged as baseline if baseline assessment is missing.

End of Study (EOS): all required phases of the study including the last scheduled procedure shown in the SoA have been completed.

A subject is considered to have completed the study if he has completed all required phases of the study including the last scheduled procedure shown in the Schedule of Activities (SoA).

The end of the study is defined as the date of last scheduled procedure shown in the SoA for the last enrolled subject or last ongoing subject in the study, whichever comes later.

Study Day will be calculated relative to the date of dose administration i.e. Study Day = Assessment Date - First Dose Date + 1, if Assessment Date is on or after First Dose Date. Assessment Date - First Dose Date, if Assessment Date is before First Dose Date.

If more than one laboratory value is available for a given study day, the last valid observation will be used in summaries, unless otherwise stated. If it is not possible to determine which is the last measurement due to missing times, then the average of all measurements for that study day will be used as the value for that study day. All observations will be presented in listings.

For subjects with duplicate self-reported symptom questionnaire or ordinal scale on the same day for the same visit, the record with the worst total score for questions 1 through 14 will be used for summary purpose. All records will be listed.

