4.11 Safety Evaluation

All safety analyses will be based upon the Safety set. All listings and tables will be presented by treatment group.

The overall observation period will be divided into 5 segments:

1. pre-treatment period: from day of patient's informed consent to the day before first dose of study medication
2. on-treatment period: from the day of first dose of study drug (D1) to the day of last dose (up to D14).
3. post-treatment period: from the day after last dose (up to D15) to D28.
4. treatment and post-treatment period: from D1 to D28.
5. safety follow up period: from D29 to D42.

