4.11.4.1 Hematology, Clinical Chemistry, and Coagulation

The following by treatment summaries will be generated separately for hematology, clinical chemistry, and coagulation laboratory tests:

- Frequency table for newly occurring on-treatment Grades 3 or 4.
- Shift tables using DAIDS grades to compare baseline to the worst on-treatment value.
- For laboratory tests where DAIDS grades are not defined, shift tables using the low/normal/high classification to compare baseline to the worst on-treatment value.
- Listing of all laboratory data with values flagged to show the corresponding DAIDS grades and the classifications relative to the laboratory normal ranges.

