Subject Diary should be completed every day since screening visit until D14 or the last dose.

Questionnaire should be completed every day since screening visit to the end of post-treatment. For details refer to Section 7.2.6.

12. Chest X-ray or CT-Scan or 12-ECG can be done per investigator's discretion. If investigator deems the result is clinically significant, the result should be recorded with eCRF.

13. Hospitalization events: if the subject is hospitalized, the treatment may be continued to the 14 days per PI. Hospitalization is defined as ≥ 24 hours in hospital of care. For details refer to Section 7.1.2.

Record if the following events occur:

- Emergency room visits
- Hospitalized
- ICU admittance
- Extended care facility admittance
- Discharge

14. Documentation from hospital records is acceptable.

Includes:

- Limitation on activities due to COVID-19
- Ongoing hospital medical care
- Supplemental oxygen
- Non-invasive ventilation or high flow oxygen device
- Mechanical ventilation
- ECMO, or

15. Adverse events: any events that occur after signing the informed consent are considered AEs as defined in Section 10.3.

16. Concomitant medications: all medications administered within 30 days prior to the first dose of study treatment through 30 days after the last dose of study treatment will be recorded in the concomitant medications, for details refer to Section 6.4.

17. Pharmacokinetics (PK) samples only need to be taken for at least 200 subjects, who will be assigned according. For details refer to Section 7.2.3.

18. All women regardless of childbearing potential must complete a serum pregnancy test at screening visit, urinary pregnancy test on day 28 as per the schedule of assessment for women of childbearing potential. Local laboratories will be used for the analysis of serum and urinary pregnancy tests.

19. Early withdrawal (EW): if the subject is early withdrawn from this study for any reason (Section 7.1.4), the subject should complete the EW visit, and the visit should occur within 2 days of the EW day. The subject will go to the safety follow-up period for additional 28 days after his last dose.

20. D42 (or 28 days ± 2 post last dose if subject is withdrawn early) safety follow-up visit is phone call visit.

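### SAP 4.11.4 contradicts SAP 4.2 on the laboratory baseline, and an on-treatment period ending at the last dose leaves some permitted end-of-treatment draws out of every laboratory table

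*SAP*

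**What the plan says.** **Baseline.** Three statements apply to the same tables.

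- SAP 4.2 sets the general rule: "Baseline: the last available pre-treatment assessment, unless otherwise specified".
- SAP 4.11.4, on screening laboratory values, says these are for judging "eligibility, and therefore it will be listed only, but not summarized in tables".
- Protocol 7.2.2 says: "For safety evaluations, baseline is defined as assessments done on Day 1 prior to the first dose of study treatment".

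SAP 4.11.4.1 then asks for "Shift tables using DAIDS grades to compare baseline to the worst on-treatment value", a matching low/normal/high shift table for tests without DAIDS grades, a frequency table of new Grade 3 or 4 values on treatment, and a listing of all laboratory data.

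**Window.** SAP 4.11 defines the "on-treatment period: from the day of first dose of study drug (D1) to the day of last dose (up to D14" at the latest), and the post-treatment period starts the next day. The Day 14 visit may be held up to Day 15 (SAP Table 4 allows one day after; protocol Table 1 allows one day either side). For early withdrawal (EW), SAP 6.1 note 19 says "the visit should occur within 2 days of the EW day". Protocol 7.1.3.1 likewise allows 2 days after permanent discontinuation for an end-of-treatment (EOT) visit. The Schedule of Activities has no column of that name, so I take the EW column to serve for it.

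**The concern.** A shift table needs a starting value, and a grade is new only relative to one. If the listing-only sentence is programmed as it stands, the single scheduled pre-dose value is unavailable to both tables. Baseline matters here. Protocol 5.3 criterion 3 joins its bilirubin, AST and ALT limits with an *and*, so it does not by itself exclude an isolated transaminase rise. The criteria also set no numerical limit for creatine kinase (CK) or blood counts.

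The window matters because laboratory data are a stated secondary (safety) endpoint. Hepatic and hematological events and raised CK are also events of special interest (SAP 4.11.3). Protocol 1.2.3.1.1 reports drug-related AST and ALT increases in 14.8% and 13.0% of subjects in one oncology study and a Grade 4 CK event in another. With so few scheduled draws per subject, leaving one out by calendar date can remove most or all of a subject's on-treatment laboratory data from the tables.

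**Working it through.** The plan gives no figure of its own on this point to reproduce. The check sets the draw schedule (protocol Table 1, SAP Table 4) against the SAP 4.11 periods.

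**Step 1: scheduled draws.**

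| Test | Screen | Day 1 | Day 7 | Day 14 | EW | Day 28 |
|---|---|---|---|---|---|---|
| Hematology, chemistry | yes | no | yes | yes | yes | yes |
| Coagulation | yes | no | no | yes | yes | yes |

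Each row has exactly one planned pre-dose draw, at screening. A subject who completes dosing has at most two scheduled on-treatment draws for hematology and chemistry, and one for coagulation.

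**Step 2: what each baseline rule yields.**

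- SAP 4.2: the screening value, for everyone who has one.
- SAP 4.11.4 read literally: no scheduled baseline in any table. The sentence covers all values from the screening phase, same-day screening included.
- Protocol 7.2.2: a Day 1 pre-dose value, which the schedule collects only when screening and Day 1 coincide (allowed by SAP 6.1 note 9).

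In that same-day case the pre-dose draw carries study day 1. SAP 4.11 opens the on-treatment period on that date, so by date alone a pre-dose value could also count as on treatment.

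**Step 3: classify permitted draw days.** Let L be the day of last dose. A draw on day d is on treatment if 1 ≤ d ≤ L and post-treatment if d > L. The EW day is taken to be day L.

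| Last dose | Day 7 visit (days 6–8) | Day 14 visit or EW visit |
|---|---|---|
| L = 14 | 6, 7, 8 on | Day 14 visit: 13 (protocol window only) and 14 on; **15 post** |
| L = 7 | 6, 7 on; **8 post** | EW visit: 7 on; **8, 9 post** |
| L = 5 | **6, 7, 8 post** | EW visit: 5 on; **6, 7 post** |

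**Step 4: scheduled on-treatment values left.**

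- Hematology and chemistry, L = 14, Day 14 visit held on Day 15: 2 − 1 = 1.
- Coagulation, same case: 1 − 1 = 0.
- All three panels, L = 5, EW draw on Day 6 or 7: 0.

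No table in SAP 4.11.4.1 covers post-treatment values, so these draws appear only in the listing. The SAP is also not uniform on Day 15: its Table 1 maps unscheduled blood samples from Days 13 to 15 to the Day 14 visit.

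**Step 5: size.** If a share f of 668 subjects had the Day 14 draw on Day 15, the number of subjects affected is 668 × f. The share is not in the documents. As an assumed range, f = 0.05 gives 33, f = 0.20 gives 134 and f = 0.50 gives 334. No count of early stops is given either.

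**The case against.** The strongest reply on baseline is that SAP 4.2 already answers the question. With no Day 1 draw, its rule selects the screening value, and the shift tables presuppose one. On this view the sentence in 4.11.4 only means that no separate screening-visit summary is shown. That is a plausible reading, and it means that loss of baseline is not certain. It does not remove the conflict: the 4.2 rule yields where something else is specified, and 4.11.4 is the specific rule for laboratory data. Protocol 7.2.2 does not settle it, because Protocol 10.1 lets the SAP prevail.

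On the window, the limit is not a SAP departure. Protocol 10.7.1 uses the same period and 10.7.3 the same tables. Early withdrawal is expected to be uncommon (Protocol 7.1.4), and a scheduled visit at which stopping is decided may serve as the EOT visit (7.1.3.1). Unscheduled draws are allowed (7.2.2.3). Clinically significant abnormalities become adverse events (8.1.3), and treatment-emergent events are tabulated through the end of study (SAP 4.11.2). All of this stands and limits the harm. The adverse-event route is not complete: Protocol 8.1.2 exempts abnormal laboratory findings tied to the underlying disease unless they are more severe than expected.

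**Conclusion.** Two wording defects stand. The SAP's baseline rules for laboratory tables contradict each other. The on-treatment period also excludes draws that the visit schedule permits. The size is unknown; the range in step 5 is illustration only.

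A reader might infer more than the documents support:

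- *The tables lose their baseline.* This follows only from the literal reading of SAP 4.11.4. Under 4.2 nothing is lost.
- *The loss falls on subjects screened the day before dosing.* Neither reading gives this: the literal one affects everyone, the other no one.
- *Many end-of-treatment draws drop out.* If dosing runs to Day 14, a draw on Day 14 (or on Day 13 under the protocol window) is kept. Only Day 15 draws, scheduled draws after an earlier last dose, and EW or EOT draws after the last dose are affected, and none of these is counted anywhere.
- *Toxicity in the active arm is understated.* The rule applies to both arms, and no difference in stopping or visit timing is given. A dropped draw can lower a subject's worst value in either arm. A missing baseline either makes a new grade impossible to determine or counts an existing abnormality as new, which overstates it.

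**What to change.** In SAP 4.11.4, replace the listing-only sentence with rules to this effect:

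- The last value before first dose, including the screening value, is the laboratory baseline for the shift and new-grade tables.
- A pre-dose draw taken on the day of first dose is baseline and is not an on-treatment value.
- For laboratory tables, the Day 14 visit draw (through Day 15) and the EW or EOT visit draw count as on treatment, assigned by visit.
- The worst-value and new Grade 3 or 4 tables are repeated over Days 1 to 28, a segment SAP 4.11 already defines.

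Align Protocol 7.2.2 with the first two rules. Assignment by visit is safer than a fixed limit such as last dose plus 2 days. The EW visit is timed from the withdrawal day, so a fixed limit misses it when withdrawal comes later than the last dose.

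The cost is SAP wording, reprogramming and a few more tables, with no new data. Some values drawn 1 to 2 days off drug will count as on treatment, or more days off drug where withdrawal follows the last dose by longer. Showing days since last dose in the listing would make this visible.
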